13.7.3 Exploratory Efficacy Analyses

All expected samples (n=80 presuming approximately 5% unevaluable rate) will be used for the exploratory analysis. The sample size justifications are based on assessing the association of TILs and response status.

Tumor Infiltrating Lymphocytes (TILs): The relationship between tumor-infiltrating lymphocytes (TILs) and study outcomes will be explored according to pre-nivolumab TIL percentages (use the mandatory biopsy specimen). It is hypothesized that higher levels of lymphocytic infiltration will be associated with better outcomes.

Arm A: With an expected samples of N=23, TILs will be descriptively summarized according to response status assessed during the first year after nivolumab discontinuation. An estimated difference of TIL score between the response groups will be summarized with 90% confidence interval.

Arm B: To examine responses according to levels of TILs, the expected samples of N=57 will be divided retrospectively according to response status (response (PR/CR) or non-response (assessed via serial image assessments after ipilimumab addition to nivolumab)). Pre-treatment percentages of stromal infiltrating lymphocytes will be summarized descriptively for the two response groups and compared using Wilcoxon rank-sum tests. Assume a targeted PR/CR rate of 20% (our primary study alternative hypothesis), if there are 11 responses (20% of 57 subjects) and 46 non-responses, a Wilcoxon rank-sum test with a two-sided, 10% type I error will have 93% power to detect a difference in pre-treatment TILs that is 1.06 times the common standard deviation.

Kaplan-Meier estimates will be used to visualize the relationship between the PFS or OS and median of the distribution of intratumoral or stromal percentages (TILs) or disease phenotype defined by TILs ($\geq 50\%$ versus $< 50\%$) in pre-treatment/baseline samples TILs. Medians of the time-to-event endpoints will be calculated with two-sided 90% CIs according to the disease phenotype groups.

Changes in TILs between pre-treatment and disease progression/treatment discontinuation will be calculated (post-pre) for patient with available biopsy samples at both timepoints and summarized descriptively.

PD-L1 Expression:

The association between pre-treatment PD-L1 expression and outcomes will be explored. The PD-L1 expression will be evaluated by IHC in both tumor cell membrane and tumor-infiltrating mononuclear cells (TIMC). It is hypothesized that higher expression levels of PD-L1 will be associated with poor outcomes, due to the fact that up-regulation of PD-L1 may allow cancers to evade the immune system.

To examine responses according to PD-L1 expression, the evaluable samples will be divided retrospectively according to study objective response or non-response. Pre-nivolumab treatment PD-L1 expression will be summarized descriptively for the two response groups.

For the samples from arm A: with the expected small sample (n=23), the analysis will be descriptive. Specifically, the proportion of patients remaining on PR or CR at 1 year since nivolumab according to pre-treatment PD-L1 positivity (PD-L1>5%) will be summarized with two-sided 90% exact, binomial confidence intervals.

For the samples from arm B: in order to assess the association of PD-L1 positivity (PD-L1+) with objective response (i.e., achieving PR or CR upon the addition of ipilimumab to nivolumab), based on a targeted ORR of 20% for this portion of study, which corresponds to have groups of non-responders (n=46) vs responders (n=11) respectively, and assuming an overall expected PD-L1+ of 50%-60% in TIMC, the following table provides the statistical power using a fisher's test to detect the PD-L1+ difference between the two response groups, with a one-side type I error of 0.05. Note, only large differences in % of PD-L1 positivity (51% in non- responder vs. 4% in responders) could be detected with at least 80% power.

Non-responders (N=46)	Responders (N=11)	
% PD-L1 + in TIMC	% PD-L1 + in TIMC	Statistical Power (Fisher's exact test)
50	5	91
60	11	91
70	17	93

In addition, the proportion of patients with objective response i.e., achieving PR or CR upon the addition of ipilimumab to nivolumab according to pre-treatment PD-L1+ will be summarized with two-sided 90% exact, binomial confidence intervals. Visualization of the relationship between baseline PD-L1 expression and the distributions of PFS or OS will employ Kaplan-Meier estimates stratified by PD-L1+. Medians of the time-to-event endpoints of PFS and OS may be shown with two-sided 90% confidence intervals.

Single Cell Sequencing:

The 25 paired samples collected at DFCI and selected sites will undergo the molecular profiles (transcriptome) assessments. The molecular profiles will be descriptively summarized for the paired samples. The exploratory analysis to assess the correlations of single cell molecular profiles with the clinical outcome may be performed.

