3.1.3 Correlative/Exploratory Objectives

- Evaluate the relationship between tumor-infiltrating lymphocytes (TILs), programmed death-ligand 1 (PD-L1) tumor expression, and other tissue biomarkers with efficacy outcomes (proportion of PR/CR, PFS, OS)
- Evaluate the relationship between PD-L1 status in archival tissue and in fresh tumor specimens
- Evaluate mechanisms of response to nivolumab in fresh tumor specimens obtained at baseline in subjects with a durable response to treatment (≥ 1 year)
- Evaluate mechanisms of intrinsic and acquired resistance to nivolumab and ipilimumab treatments in fresh tumor specimens obtained at time of radiographic progression
- Assess molecular mechanisms of resistance to treatment via circulating free DNA (cfDNA) assessment and to correlate cfDNA molecular profile with metastasis biopsy molecular profile
- Assess molecular mechanisms of resistance to treatment via circulating tumor cell (CTC) assessment
- Correlate CTC molecular profile with metastasis biopsy molecular profile

- Assess mechanisms of response and resistance to treatment via single cell molecular assessment (transcriptome assessment)
- Correlate single cell molecular profile with metastasis biopsy molecular profile

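### Section 13.7.3 relates baseline TILs and PD-L1 to PFS and OS only through descriptive curves on two-group markers, so this part of objective 3.1.3 yields no effect estimate and does not use the recorded percentage

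*Combined protocol and SAP*

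**What the plan says.** Section 3.1.3 sets an exploratory objective to relate TILs, PD-L1 and "other tissue biomarkers with efficacy outcomes (proportion of PR/CR, PFS, OS"). Section 13.7.3 serves the PFS and OS part of it as follows.

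- **TILs:** Kaplan-Meier curves are to "visualize the relationship between the PFS or OS and median of the distribution of intratumoral or stromal percentages (TILs"), or a phenotype defined as at least 50% versus below 50%. Then: "Medians of the time-to-event endpoints will be calculated with two-sided 90% CIs according to the disease phenotype groups".
- **PD-L1:** "Visualization of the relationship between baseline PD-L1 expression and the distributions of PFS or OS will employ Kaplan-Meier estimates stratified by PD-L1" positivity; group medians may be shown with 90% intervals. The positivity cut appears in the Arm A paragraph as "pre-treatment PD-L1 positivity (PD-L1>5"%).

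No log-rank test, hazard ratio, regression model or power figure is given for either marker against PFS or OS.

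For response, the same section keeps TILs on their scale: a Wilcoxon rank-sum test on the percentages in Arm B and a difference in TIL score with a 90% interval in Arm A. The section says its sample-size justification rests on TILs and response.

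**The concern.** The objective asks about a relationship, and the stated hypotheses are graded: more infiltration, better outcome; more PD-L1, worse outcome. Two curves and two medians do not estimate a gradient. They give no single measure of association with an interval, and they treat all subjects on one side of the cut as alike.

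The section thus handles one marker in two ways, continuous for response and dichotomised for PFS and OS, without giving a reason. Two TIL cuts, and intratumoral or stromal percentages, are offered without saying which display is the main one.

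At stake is how much the study can report about markers and time-to-event outcomes from about 57 subjects in Arm B and 23 in Arm A. No primary or secondary conclusion is affected.

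**Working it through.** **1. The plan's own figures (response analyses).** Inputs from Section 13.7.3: 11 responders, 46 non-responders, a difference of 1.06 SD, two-sided 10%.

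Power = Φ(1.06 × √(46 × 11 / 57) − 1.645) = Φ(3.158 − 1.645) = Φ(1.513) = 93.5%. Multiplying the effect term by √(3/π) for the rank test gives Φ(3.086 − 1.645) = 92.5%. The plan states 93%, which reproduces. The Arm B PD-L1 table also reproduces with a one-sided Fisher test: 90.7%, 90.8% and 93.3% against the stated 91, 91 and 93. There is no corresponding figure for PFS or OS to reproduce.

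**2. Information kept by a split.** Assumption: linear log-hazard in the marker. The share kept is the squared correlation between the marker and the two-group indicator, with a fraction p above the cut:

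- any marker: p(1 − p)(m₁ − m₀)² / variance, where m₁ and m₀ are the means above and below the cut;
- normal marker: φ(z)² / [p(1 − p)], which is 2/π = 0.637 at the median.

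**3. Illustrative power.** Suppose a test on the continuous marker has 80% power at two-sided 10%, the level the plan uses for TILs and response. After the split, power = Φ(√kept × (1.645 + 0.842) − 1.645).

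| Marker and cut | Information kept | Power after split |
|---|---|---|
| Uniform, median | 0.75 | Φ(2.153 − 1.645) = 69% |
| Normal, median | 0.637 | Φ(1.984 − 1.645) = 63% |
| Normal, 60/40 | 0.622 | 62% |
| Normal, 20/80 | 0.49 | 54% |
| Exponential, median | 0.48 | 53% |

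At two-sided 5% the normal, median-split figure is Φ(0.798 × 2.802 − 1.960) = 61%. At two-sided 10% the loss for a normal marker split at its median depends on the starting power: 7.4 points from 30%, 13.0 from 50%, 16.7 from 80%, 11.4 from 95%.

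**4. Simulation check.** N = 57, two-sided 10%, Cox score test on the continuous marker against a log-rank test at the median. Event counts and hazard ratios are assumed.

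| Events | HR per SD | Normal marker | Uniform marker |
|---|---|---|---|
| about 39 | 1.48 | 75.8% to 56.5% | 75.0% to 63.8% |
| about 51 | 1.42 | 74.2% to 57.1% | 75.7% to 62.9% |

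The losses are 17 to 19 points for a normal marker and 11 to 13 for a uniform one.

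**5. Precision of a Cox estimate.** For a standardised marker the variance of the log hazard ratio is roughly 1/events, so the 90% limits are the estimate divided and multiplied by exp(1.645/√events). With 40 events in Arm B the factor is exp(0.260) = 1.30. In Arm A, even if all 23 subjects had events, it is exp(0.343) = 1.41; with 12 events it is exp(0.475) = 1.61.

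**6. PD-L1 scale.** The plan is "assuming an overall expected PD-L1+ of 50%-60% in TIMC". If the 5% cut also defines positivity in these cells, 40% to 50% of subjects lie at or below 5% on a 0 to 100 scale. That points to strong skew, so a hazard ratio per raw percentage point would be a poor summary.

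**The case against.** The strongest reply is that these are displays in an exploratory section. The plan's own verb is to visualise; no test, decision rule or power is attached; and the sample-size argument concerns response, where TILs stay continuous. This stands: no planned test loses power, and the figures above compare two hypothetical tests.

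The continuous model also needs log-linearity, and a percentage crowded near zero, as PD-L1 may be, does not meet it without a transformation. That stands too and shapes the fix.

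Several stronger readings are tempting, and the documents do not support them:

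- **The split always costs at least a third of the information, or at least 18 points of power.** The first needs a roughly normal marker; the documents give no distribution, and a uniform one loses 25%. The second is not a floor: most of the losses above are smaller.
- **The TIL cut will be picked after the curves are seen.** The wording allows two displays, and the reported medians are tied to the phenotype groups. The main display is unnamed; selection after the fact is not shown.
- **Each display will compare about 28 or 12 subjects per group.** The sentence on TIL curves does not say it is by arm, and the section opens with all 80 samples.
- **Overlapping median intervals will be read as no relationship.** The plan sets no overlap rule.

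None of this supplies the missing estimate: the time-to-event part of the objective still ends without a measure of association.

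**Conclusion.** The point holds as a modest gap. For PFS and OS, both markers enter only as two groups, and the output is curves and group medians. No effect estimate is planned and the recorded percentage is not used, in contrast to TILs and response.

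As an illustration of size, a median split of a roughly normal marker keeps about 64% of the information, and 80% power would become about 63% if a two-sided 10% test were run. The loss is smaller for a uniform marker and larger for strongly skewed markers or uneven cuts. The marker distribution, the linear log-hazard, the event count and the hazard ratio are assumptions. The missing estimate does not depend on them.

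**What to change.** In Section 13.7.3:

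1. Keep the Kaplan-Meier curves as displays. Name one TIL cut as the main display and say whether it uses the intratumoral or the stromal percentage.
2. Add, within each arm, an exploratory Cox estimate of the hazard ratio for PFS and for OS per SD, or per 10 percentage points, of baseline TILs, with a two-sided 90% interval. Fitting by arm also respects the different time origins in Section 13.2.2: nivolumab discontinuation in Arm A, ipilimumab initiation in Arm B.
3. Do the same for PD-L1 percentage on a transformed scale stated in advance that handles zeros and skew, for example log(x + 1).
4. State that log-linearity will be checked with residual plots.

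The cost is SAP wording and one model per marker, endpoint and arm, on data already collected. The downsides are the log-linearity assumption and wide intervals in Arm A, which should be reported as such.

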14. DATA REPORTING/REGULATORY REQUIREMENTS

Adverse event lists, guidelines, and instructions for AE reporting can be found in Section 12 (Adverse Events).

14.1 Data Reporting

14.1.1 Method

The Office of Data Quality (ODQ) will collect, manage, and perform quality checks on the data for this study.

14.1.2 Responsibility for Data Submission

Investigative sites within DF/HCC or DF/PCC are responsible for submitting data and/or data forms to the Office of Data Quality in accordance with DF/HCC SOPs.

14.2 Data Safety Monitoring

The DF/HCC Data and Safety Monitoring Committee (DSMC) will review and monitor toxicity and accrual data from this study. The committee is composed of clinical specialists with experience in oncology and who have no direct relationship with the study. Information that raises any questions about participant safety will be addressed with the Overall PI and study team.

The DSMC will review each protocol up to four times a year or more often if required to review toxicity and accrual data. Information to be provided to the committee may include: up-to-date participant accrual; current dose level information; DLT information; all grade 2 or higher unexpected adverse events that have been reported; summary of all deaths occurring within 30 days of intervention for Phase I or II protocols; for gene therapy protocols, summary of all deaths while being treated and during active follow-up; any response information; audit results, and a summary provided by the study team. Other information (e.g. scans, laboratory values) will be provided upon request.

14.3 Multicenter Guidelines

This protocol will adhere to the policies and requirements of the DF/HCC Multi-Center Data and Safety Monitoring Plan. The specific responsibilities of the Overall PI, Coordinating Center, and Participating Institutions and the procedures for auditing are presented in Appendix D.

- The Overall PI/Coordinating Center is responsible for distributing all IND Action Letters or Safety Reports to all participating institutions for submission to their individual IRBs for action as required.
- Mechanisms will be in place to ensure quality assurance, protocol compliance, and adverse event reporting at each site.
- Except in very unusual circumstances, each participating institution will order the study agent(s) directly from supplier. A participating site may order the agent(s) only after the initial IRB approval for the site has been forwarded to the Coordinating Center.

14.4 Data Quality Oversight Activities

Validation of data will be completed on a continual basis throughout the life cycle of the study. A summary report (QC Report) of these checks together with any queries resulting from manual review of the eCRFs will be generated for each site and transmitted to the site and the site monitor. Corrections will be made by the study site personnel.

There will be at least one routine visit per site per year for sites that have accrued. Additional for cause visits may occur as necessary. Source documents will be reviewed for verification of agreement with data entered into InForm. It is important for the site investigator and their relevant personnel to be available for a sufficient amount of time during the monitoring visits or audit, if applicable. The site investigator and institution guarantee access to source documents by the sponsor/investigator or its designee.

14.5 Compliance with Trial Registration and Results Posting Requirements

Under the terms of the Food and Drug Administration Modernization Act (FDAMA) and the Food and Drug Administration Amendments Act (FDAAA), the sponsor-investigator of the trial is solely responsible for determining whether the trial and its results are subject to the requirements for submission to the Clinical Trials Data Bank, <http://www.clinicaltrials.gov>. All results of primary and secondary objectives must be posted to CT.gov within a year of completion. Information posted will allow subjects to identify potentially appropriate trials for their disease conditions and pursue participation by calling a central contact number for further information on appropriate trial locations and study site contact information.

15. DATA HANDLING AND RECORD KEEPING

15.1 Data Management

The Dana-Farber Cancer Clinical Trials Office will provide Project Management and Monitoring services for this trial. Data will be collected through the web based clinical research platform, InForm, a system compliant with Good Clinical Practices and Federal Rules and Regulations created by the Clinical Trials Research Informatics Office (CTRIO). All data will be collected and entered into InForm by study site personnel from participating institutions.

Before trial completion, it is permissible to report data on a subset of patients regarding safety, specific cohorts that complete accrual and mature earlier than the overall trial, or results from cohorts that were added mainly for correlative purposes such as the single cell sequencing cohort.

15.2 Case Report Forms and Submission

Generally, clinical data will be electronically captured in InForm and correlative results will be captured in spreadsheets or other secure database(s). If procedures on the study calendar are performed for standard of care, at minimum, that data will be captured in the source document. Select standard of care data will also be captured in InForm, according to study-specific objectives.

The completed dataset is the sole property of the sponsor-investigator's institution and should not be exported to third parties, except for authorized representatives of appropriate Health/Regulatory Authorities, without permission from the sponsor-investigator.

15.3 Record Retention

To enable evaluations and/or audits from Health Authorities, the site investigator agrees to keep records, including the identity of all subjects (sufficient information to link records; e.g., hospital records), all original signed informed consent forms, copies of all source documents, and detailed records of drug disposition. All source documents are to remain in the subject's file and retained by the site investigator in compliance with the site contract. No records will be destroyed until the sponsor/investigator confirms destruction is permitted.

15.4 Confidentiality

There is a slight risk of loss of confidentiality of subject information. All records identifying the subjects will be kept confidential and, to the extent permitted by the applicable laws and/or regulations, will not be made publicly available. Information collected will be maintained on secure, password protected electronic systems. Paper files that contain personal information will be kept in locked and secure locations only accessible to the study site personnel.

Subjects will be informed in writing that some organizations including the sponsor-investigator and his/her research associates, BMS, IRB, or government agencies, like the FDA, may inspect their medical records to verify the information collected, and that all personal information made available for inspection will be handled in strictest confidence and in accordance with local data protection laws. If the results of the study are published, the subject's identity will remain confidential.

16. PUBLICATION PLAN

The data will be collected by the investigators and analyzed by the co-principal investigators and the statistical team at DFCI. It is anticipated that the results will be made public within 12 months of the end of data collection. A report is planned to be published in a peer-reviewed journal, however initial release may be an abstract that meets the requirements of the International Committee of Medical Journal Editors. [REDACTED] in consultation with [REDACTED]. [REDACTED] as well as outside investigators will decide on the authorship orders for abstracts and manuscripts from the trial.

18. APPENDICES

A. Performance Status Criteria

B. Information on Possible Drug Interactions

C. Management Algorithms for Immune-Mediated Adverse Events

D. Dana-Farber/Harvard Cancer Center Multi-Center Data and Safety Monitoring Plan

19. APPENDIX A: PERFORMANCE STATUS CRITERIA

ECOG Performance Status Scale		Karnofsky Performance Scale	
Grade	Descriptions	Percent	Description
0	Normal activity. Fully active, able to carry on all pre-disease performance without restriction.	100	Normal, no complaints, no evidence of disease.
		90	Able to carry on normal activity; minor signs or symptoms of disease.
1	Symptoms, but ambulatory. Restricted in physically strenuous activity, but ambulatory and able to carry out work of a light or sedentary nature (e.g. , light housework, office work).	80	Normal activity with effort; some signs or symptoms of disease.
		70	Cares for self, unable to carry on normal activity or to do active work.
2	In bed <50% of the time. Ambulatory and capable of all self-care, but unable to carry out any work activities. Up and about more than 50% of waking hours.	60	Requires occasional assistance, but is able to care for most of his/her needs.
		50	Requires considerable assistance and frequent medical care.
3	In bed >50% of the time. Capable of only limited self-care, confined to bed or chair more than 50% of waking hours.	40	Disabled, requires special care and assistance.
		30	Severely disabled, hospitalization indicated. Death not imminent.
4	100% bedridden. Completely disabled. Cannot carry on any self-care. Totally confined to bed or chair.	20	Very sick, hospitalization indicated. Death not imminent.
		10	Moribund, fatal processes progressing rapidly.
5	Dead.	0	Dead.

